Matrix metalloproteinases cause endometrial fragility, irregular vessel breakdown, influx of leukocytes, and bleeding. [15, 16] Tetracyclines inhibit matrix metalloproteinase activity independent of their antimicrobial action, with doxycycline being the most potent inhibitor among the tetracyclines [17, 18]. Doxycycline also treats Chlamydia and Ureaplasma infection, which may cause chronic endometritis that presents as abnormal uterine bleeding [19]. A pilot study by Weisberg [21] reported a 50% reduction in ESI-related bleeding duration with doxycycline for 5 days but no long-term improvement and no improvement over placebo in a follow-up study [22]. Doxycycline anti-inflammatory effects are dependent on dose and treatment duration *in vitro* [20] thus supporting a longer therapy course. Clinically there is no precedent for increasing dose beyond 100 mg BID. While there is a clinical precedent for using 10 days of treatment, there is not for 5 days of use. This length of administration was likely used in the Weisberg studies(21,22) for blinding purposes [21,22].In our retrospective cohort (N=9), 10 day course of Doxycycline resulted in bleeding improvement and method continuation in 66% of patients who reported unacceptable bleeding.[3,7] Of 36 untreated patients, 25 (70%) requested early ESI removal.[7]

The published experience with Doxycycline in the treatment of unacceptable bleeding associated with ESI is limited to small, retrospective studies. The validation and subsequent clinical implementation of an evidence-based cost-effective treatment is likely to dramatically increase the acceptability and continuation rates of ESI.

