If a patient reports bleeding concerns as described in section 5.2.1 and is randomized to the placebo group, she will be given a pill bottle containing placebo made to look identical to treatment to be taken twice daily for 10 days. Patient and investigators will be blinded as to group assignment.

d. Doxycycline group

If patient has bleeding concerns determined in section 5.2.1 and is randomized to the Doxycycline group, she will be given a pill bottle containing Doxycycline 100 mg to be taken twice daily for 10 days. Patient and investigators will be blinded as to group assignment. Patients who experience unacceptable bleeding but are not bleeding at the time of study personnel contact will be instructed to call back if unacceptable bleeding recurs for randomization to treatment or placebo.

e. Treatment compliance process

Pill counts at the end of each treatment course will be performed to assess patient compliance with treatment. A pill diary given to patients at the time of randomization will provide temporal correlation between treatment initiation and bleeding symptoms.

f. Symptom recording

Upon enrollment and ESI insertion, patients will begin a weekly prospective symptom diary in order to self-assess bleeding and additional symptoms for a **total of 39 weeks from study enrollment**. A modification of the PBLAC where 1= no bleeding, 2=spotting requiring 1-2 panty-liners per 24 hours only, 3= bleeding requiring 1-3 tampons/pads in 24 hours, 4=bleeding requiring 4-6 tampons/pads per 24 hours, and 5=bleeding requiring >6 tampons/pads per 24 hours will be utilized for bleeding recording.[27] Bleeding diaries will be collected every 13 weeks and completion will be required for continued enrollment in the study and receipt of remuneration after every 13 week interval. Patients will also record any other associated symptoms such as headache, mood changes, acne and intolerance to treatment detailed in sections 6.2.2 and 6.2.3. Prospective symptom diary can be captured on a paper formate or via Mayo Clinic website RED Cap.

A bleeding episode is defined by the WHO as any set of one or more bleeding days (either consecutive or separated by only one bleeding-free day) bounded at each end by two or more bleeding-free days. **The bleeding pattern will be analyzed within each 13-week reference period** and categorized into 6 groups [4, 13, 14]:

- Amenorrhea (no bleeding during the reference period),
- Infrequent bleeding (fewer than 3 bleeding episodes),

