- Normal bleeding frequency (3-5 bleeding episodes).
- Frequent bleeding (more than 5 bleeding episodes),
- Prolonged bleeding (1 or more bleeding episodes lasting 14 days or more)

Subgroup analysis may provide additional insight into the efficacy of treatment for various bleeding patterns.

g. Patient satisfaction surveys

Patients will be asked to fill out short satisfaction surveys at randomization measuring satisfaction prior to any treatment, and at 13 and 26 weeks post randomization (see appendix). If patient has their ESI removed prior to 26 weeks post randomization, she will be given a final satisfaction survey at removal. Patient satisfaction surveys will be recorded on a paper formate or via Mayo Clinic website RED Cap.

Patients will rate their satisfaction with a) ESI and b) bleeding with ESI on a 5-point Likert scale ranging from very satisfied to very dissatisfied. If patient has ESI removed prior to 26 weeks post-study enrollment, she will be given a final satisfaction survey at removal.

h. Treatment issues

At enrollment, patients will be provided with a contact number allowing them to reach study personnel at all times with concerns. Instructions will be provided for instances of drug intolerance/allergy, heavy bleeding or other ESI related issues and clinical appointments for evaluation scheduled as needed.

i. Secondary Treatment

If a patient reports unacceptable bleeding at >4 weeks post randomization to treatment or placebo, study participation will be recorded as **need for additional treatment, and will represent the primary endpoint**. If she wishes to have secondary treatment, she will be treated with Doxycycline. Treatment will be limited to two interventions per 13 week

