5.3.2 Outcome measurements

A. Primary treatment efficacy and safety end point (primary endpoint addressing specific aim #1)

- The efficacy of Doxycycline on ESI-related bleeding will be compared to placebo based on rates of **unacceptable bleeding** and weekly prospective symptom diary at 13 weeks post-randomization.

B. Primary treatment efficacy and safety endpoints (secondary endpoints addressing specific aim #1)

- Method continuation rate at 13 weeks post-randomization will be compared for women in the Doxycycline vs. placebo group.
- Bleeding patterns will be quantified based on the PBLAC and WHO classification of clinically important bleeding patterns over each 13 week reference period.[13,14, 29].
- Incidence of additional symptoms including acne, headache, mood changes in the treatment groups will be compared to placebo at randomization and 13 weeks post-randomization based on the weekly prospective symptom diary
- Interval to recurrence of unacceptable bleeding post-randomized treatment (i.e., need for additional treatment) will be determined
- Rate of adverse events associated with medical treatment will be documented by prospective symptom diary and BMI calculation. These include headache, mood changes, acne and change in BMI.

C. Patient satisfaction with primary treatment endpoint (primary endpoint addressing specific aim #2)

- Patient satisfaction with ESI at randomization for a baseline pre-treatment satisfaction and at 13 weeks post-randomized treatment following primary treatment with Doxycycline vs. placebo will be compared

D. Patient satisfaction with secondary treatment endpoint (primary endpoint addressing specific aim #2)

- Patient satisfaction with ESI at 26 weeks post-randomized treatment for patients with continued unacceptable bleeding following primary treatment who receive secondary treatment with Doxycycline will be calculated.

E. Secondary treatment efficacy and safety endpoint (primary endpoint addressing specific aim #3)

- Method continuation rate at 26 weeks post-randomized treatment for patients with continued unacceptable bleeding after primary treatment who undergo secondary treatment with Doxycycline will be calculated

F. Secondary treatment efficacy and safety endpoint (secondary endpoints addressing specific aim #3)

- Rate of ESI removal for bleeding between 13 and 26 weeks post randomization.

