5.4.1 Power statements

Based on prior Mayo data, we anticipate about 30% of patients will develop unacceptable bleeding following ESI insertion.[3,29] These patients will be approached for participation in this study. The study plans to randomize a total of 100 patients with unacceptable bleeding to either placebo (N=50) or Doxycycline (N=50). The following calculations were based on a two-sided chi-square test with a type I error rate of 0.05.

Aim 1: Of the patients with bleeding concerns, based on our prior experience we anticipate that 44% of the patients randomized to Doxycycline will request additional treatment, and about 80% in the placebo arm. We are purposely overestimating the placebo effect over that noted in our cohort (92% removal requests) to allow for variation in the study group. Given the sample size of 50 per treatment arm, the study will have >90% power to detect the anticipated difference in the need for additional treatment.

Aim 2: Across the two arms, we anticipate that 66 of the 100 patients will request additional treatment and will receive additional treatment with Doxycycline. Within this subset we plan to estimate the method continuation rate following additional treatment. Based on a sample size of 66, the ½ width for a 95% CI around an estimate of 75% is ±10%.

Aim 4: Among the anticipated 66 patients who will request additional treatment for continued unacceptable bleeding at 26 weeks post-ESI insertion, we plan to quantify the patient satisfaction rate. If we assume 75% will be “very satisfied” or “satisfied”, then the ½ width for a 95% CI around this estimate will be ±10%.

5.4.2 Proposed Statistical Analysis:

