Patients will be analyzed according to their randomized treatment arm. All calculated p-values will be two-sided and p-values less than 0.05 will be considered statistically significant. Analyses will be performed using SAS software package (version 9.2). Comparisons of categorical endpoints (e.g. need for additional treatment, bleeding pattern based on the WHO classification, presence of adverse event(s), satisfaction survey questions) between the two arms will be evaluated using the chi-square test. Additional comparisons of these endpoints, adjusted for potential confounders, will be assessed by fitting separate logistic regression models. Time-to-event methodology (e.g. Kaplan-Meier method and Cox proportional hazards regression models) will be utilized for binary versions of these endpoints if patient follow-up becomes an issue and patients don't comply with the planned follow-up before completing the study. Poisson regression models will be used to compare the diary responses between the treatment arms. In the Poisson model, the endpoint will be the number of bleeding and spotting days per patient (and likewise the number of days with additional symptoms), offset by the total days of diary follow-up per patient. Ninety-five percent confidence intervals (95% CI) will be constructed around the estimates for method continuation and satisfaction.

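### As written, the Poisson comparison of bleeding days includes diary time before randomization and after open-label doxycycline, which pulls the drug-versus-no-drug ratio toward 1 if doxycycline works

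*Combined protocol and SAP*

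**What the plan says.** - **Diary model (5.4.2).** Arms are compared as randomized by Poisson regression: "the endpoint will be the number of bleeding and spotting days per patient", offset by each woman's total diary time. No start date, end date or cut at secondary treatment is given.
- **Diary period (5.3.1.f, 7.1).** Recording is weekly, starts at insertion, and continues to 26 weeks after randomization. Randomization takes place at the week-13 contact or at any later self-report (5.3.1.b).
- **WHO patterns.** Section 5.3.1.f says "The bleeding pattern will be analyzed within each 13-week reference period", and 5.3.2.B says "Bleeding patterns will be quantified based on the PBLAC and WHO classification of clinically important bleeding patterns over each 13 week reference period". Neither says when the first period begins.
- **Secondary treatment (5.2.1, 5.3.1.i).** A woman in either arm who reports unacceptable bleeding more than 4 weeks after randomization reaches the primary endpoint. Then, "If she wishes to have secondary treatment, she will be treated with Doxycycline", unblinded. Two interventions are allowed per 13-week interval, so the randomized and open-label courses can fall in the same one.
- **Planning rates (5.4.1).** "44% of the patients randomized to Doxycycline will request additional treatment, and about 80% in the placebo arm".
- **Diary time point (5.3.2.A).** The efficacy outcome for aim 1 refers to the diary at 13 weeks after randomization. The model in 5.4.2 does not repeat that limit.

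**The concern.** The diary is the record on which section 8.1 relies for objectivity, because the primary endpoint depends on each woman's own judgement that her bleeding is unacceptable. As specified, the diary count can contain three kinds of time: before randomization, when the arms do not differ by treatment; after randomization with only the assigned course taken; and after open-label doxycycline, expected more often in the placebo arm. The first and third kinds both shrink a real difference.

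The primary endpoint counts only requests made more than 4 weeks after randomization, so the diary is the main record of what happens in weeks 1-4. No planned analysis looks at that window separately, although it is the one stretch that open-label drug cannot reach.

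**Working it through.** **1. The plan's own figures.** Section 5.4.1 states: "The following calculations were based on a two-sided chi-square test with a type I error rate of 0.05". With 50 per arm, 44% versus 80% gives 97.0% power (95.2% with Fisher's exact test), so the stated power above 90% reproduces. It concerns the primary endpoint, not the diary. The same rates imply 50 × 0.44 + 50 × 0.80 = 22 + 40 = 62 women needing further treatment, not the 66 stated in 5.4.1. The check below uses the 44% and 80%.

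**2. Share of diary time after open-label drug, weeks 0-13.** If all crossover is at week 4: placebo 0.80 × 9/13 = 55%, doxycycline 0.44 × 9/13 = 30%. If spread evenly over weeks 4-13 (on average 4.5 weeks remain): placebo 0.80 × 4.5/13 = 28%, doxycycline 0.44 × 4.5/13 = 15%. In weeks 0-4 it is zero in both arms.

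**3. Effect on the 13-week ratio.** The documents give no bleeding-day rate, so these are assumptions: one course multiplies the rate by RR for the rest of the window; crossover is on day d; everyone counted as needing treatment takes it and stays in the study.

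- m = (d + (91 − d) × RR)/91
- Placebo rate = 0.20 + 0.80 × m
- Doxycycline rate, case A (second course adds nothing) = RR
- Doxycycline rate, case B (second course multiplies the rate by RR again) = RR × (0.56 + 0.44 × m)

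Example, RR = 0.50 and d = 35: m = (35 + 28)/91 = 0.692; placebo = 0.754. Case A: 0.500/0.754 = 0.66. Case B: 0.432/0.754 = 0.57.

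| True RR | Crossover day | Case A | Case B |
|---|---|---|---|
| 0.50 | 35 | 0.66 | 0.57 |
| 0.50 | 49 | 0.61 | 0.55 |
| 0.50 | 63 | 0.57 | 0.53 |
| 0.70 | 35 | 0.82 | 0.75 |
| 0.70 | 63 | 0.76 | 0.73 |

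For a true 0.50, the loss of log effect, 1 − ln(observed)/ln(0.50), is 41% to 19% in case A and 20% to 9% in case B.

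**4. Longer windows, true 0.50.** Crossover is either all at week 4 or spread over weeks 4-13 (average week 8.5).

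- Weeks 0-26, case A: 13/(26 − 0.80 × 22 × 0.5) = 13/17.2 = 0.76, or 13/(26 − 0.80 × 17.5 × 0.5) = 13/19 = 0.68.
- Weeks 0-26, case B: 0.5 × (26 − 0.44 × 22 × 0.5)/17.2 = 10.58/17.2 = 0.62, or 0.5 × (26 − 0.44 × 17.5 × 0.5)/19 = 11.075/19 = 0.58.
- Adding 13 pre-randomization weeks at the untreated rate, case A: 26/30.2 = 0.86, or 26/32 = 0.81. Case B: 23.58/30.2 = 0.78, or 24.075/32 = 0.75.

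**5. Short-acting courses.** If each course acts for only 4 weeks (RR 0.50), the 13-week ratio without crossover is (13 − 4 × 0.5)/13 = 0.85. With crossover it is (13 − 2 − 0.44 × 2)/(13 − 0.80 × 2) = 10.12/11.4 = 0.89. Crossover then costs little; most of the distance from 0.50 is the true 13-week average.

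**6. Straddling.** If 13-week periods run from insertion, a woman randomized at week 20 has a second period (weeks 14-26) with roughly half its time before treatment. With a half-and-half split and no crossover, a true 0.50 in day counts becomes (6.5 + 3.25)/13 = 0.75. This illustrates day counts, not the WHO categories themselves.

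**The case against.** The strongest reply is that comparison by randomized arm is a proper comparison of two strategies: doxycycline first or placebo first, with open-label treatment as needed in both. That stands once pre-randomization days are excluded. Shrinkage is a defect only if the ratio is read as drug versus no drug, and with no drug effect there is nothing to shrink.

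Other points also stand:

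- The 80% was set with reference to removal requests. Women who have the implant removed end participation and add no crossover time, and secondary treatment is given only to those who want it.
- Crossover in the doxycycline arm offsets part of the dilution, as case B shows.
- Section 5.3.2.A points to 13 weeks after randomization, so the authors may have intended that window. Section 5.4.2 still does not state it.
- Collecting diaries every 13 weeks is a logistics schedule. It does not show that WHO periods start at insertion; the gap is an unstated start point.

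A reader might infer from section 4.0 that prior evidence shows a short-lived effect, since a pilot study "reported a 50% reduction in ESI-related bleeding duration with doxycycline for 5 days but no long-term improvement". The same sentence goes on to say that a follow-up study found no improvement over placebo, and the section uses the 5-day course in those studies to argue for a longer one. This does not establish a short-lived effect. It only makes a separate look at weeks 1-4 informative.

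**Conclusion.** The point holds as a gap in specification. Section 5.4.2 as written counts diary days that precede randomization and days after open-label doxycycline. If doxycycline works, both move the drug-versus-no-drug ratio toward 1, and every scenario worked above moves that way.

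The size is illustrative. It depends on the assumed effect, its duration, the timing of crossover and what a second course does. Over 13 weeks with a lasting effect, a true 0.50 appears as about 0.66-0.57 (case A) or 0.57-0.53 (case B), and a true 0.70 as about 0.82-0.76 or 0.75-0.73. Dilution is larger if 26 weeks or pre-randomization days are counted, and smaller if courses act briefly or women choose removal instead of crossing over.

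Two stronger readings are not supported. One is that the trial's main result is diluted: need for additional treatment is unaffected, because the request that leads to crossover is itself that endpoint. The other is that weeks 1-4 should replace the 13-week diary comparison: aim 1 is set at 13 weeks, and the 13-week contrast validly compares the two strategies once it starts at randomization.

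**What to change.** In sections 5.3.1.f and 5.4.2:

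1. Start the Poisson count, its offset and the WHO reference periods at randomization.
2. Adjust the Poisson model for the number of bleeding and spotting days in the 4 weeks before randomization, taken from the existing diary.
3. Keep the 13-week comparison by randomized arm, labelled as including open-label doxycycline.
4. Add a prespecified supportive comparison over weeks 1-4 after randomization, before secondary treatment is allowed.

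The cost is wording, with no added visits or diaries, and it should be settled before unblinding. The diary form is not among the documents. Because recording is weekly, the team should confirm that day counts can be split at randomization, and state a rule for the week in which it falls. The 4-week window has fewer days per woman and includes the 10-day treatment course, so it measures early effect only.

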6.0 Adverse events

An adverse event is any untoward medical occurrence in a study subject which does not necessarily have a causal relationship with the medicinal product. This includes any unfavorable and unintended sign (including an abnormal, clinically significant laboratory finding), symptom, or disease temporally associated with the use of a medicinal product, whether or not related to the medicinal product. It also includes any pre-existing condition that increases in intensity or severity or any new events after the patient has given informed consent.

6.1 Serious Adverse Events:

A serious adverse event is any untoward medical occurrence that results in one of the following:

- Death
- Life threatening illness or injury
- Permanent impairment of a body function or structure
- Inpatient hospitalization or prolongation of existing hospitalization;
- Medical or surgical intervention to prevent permanent impairment
- Fetal distress, fetal death, congenital abnormality, or birth defect

6.2 Unanticipated Adverse Device Effects:

Any serious adverse effect on health or safety, any life-threatening problem or death caused by, or associated with a device, if that effect, problem, or death was not previously identified in nature, severity, or degree of incidence in the application; or any other unanticipated serious problem associated with a device that relates to the rights, safety, or welfare of subjects.

6.2.1 Anticipated Adverse Effects of ESI insertion

- Pain at insertion site
- Infection at insertion site
- Non-insertion
- Deep insertion (non-palpable implant)
- Pregnancy at time of insertion

The above is minimized by strict adherence to the ESI insertion technique in the ESI prescribing information [4] including exclusion of pregnancy.

6.2.3 Anticipated Adverse Drug Reactions of Doxycycline

Serious side-effects include

- pseudotumor cerebri (rare)
- seizure
- swelling of face, lips, tongue, or throat
- headache
- wheezing
- chest tightness
- fever

Other side effects include

- abdominal pain
- Nausea or vomiting.
- Diarrhea
- loss of appetite.
- vaginal yeast infection
- skin itching and sensitivity to the sun
- cough

6.3 Reporting of Adverse Events:

All adverse events will be recorded on the case report forms. Serious adverse events forms must be completed and faxed to ESI clinical affairs within 3 days of knowledge of

the event. Unanticipated adverse device effect and/or unanticipated adverse drug reaction forms must be completed and faxed to ESI Clinical Affairs within 24 hours of knowledge of the event.

6.4 Data and Safety Monitoring Plan

The ESI device was FDA approved in 2006 with no major morbidity or mortality reported to date. Further, its efficacy in preventing pregnancy is > 99%. [4] In over 300 procedures performed at Mayo, no complications of insertion or removal have been noted. All practitioners involved in ESI insertion and removal have successfully completed the FDA mandated training. Further, the principal investigator and Co-Investigators, Drs. [name], [name] and [name] will monitor the safety of the subjects and are available on call 24 hours, 7 days a week. A review of the complications data will be performed after the enrollment of 50 patients; any unexpected complication or major complication will prompt the PI to notify the IRB.

7.0 Ethical Considerations (Human Studies):

Informed consent will be obtained in the Mayo standard written form. Since the interventions are a component of routine clinical practice, we do not anticipate any ethical issues or risks beyond what is currently deemed as acceptable for standard practice. All insertion and removal procedures will be performed by practitioners who have completed the FDA mandated training program. The risks of medical therapy are detailed in sections 6.2.2 and 6.2.3.

